7.3 Safety

1) American Diabetes Association (ADA) Severe Hypoglycemic AE

A hypoglycemic AE will be classified as "ADA severe" if the answer to the question "Was third party intervention required for this episode of hypoglycemia?" is Yes on the Hypoglycemia CRF page as mentioned in the ADA hypoglycemia position statement (3).

ADA Severe Hypoglycemic AE should not be confused with hypoglycemia AEs that are graded severe (Grade 3) per National Cancer Institute Common Terminology Criteria for Adverse Events (NCI CTCAE) grade (see Section 11.8.1.1).

2) Adverse Event Leading to Discontinuation of IP

An AE will be classified as an AE leading to discontinuation of IP if the answer to the question "Did the adverse event cause the subject to be discontinued from the study?" is Yes on the AE CRF page.

3) Hypoglycemic AE

An AE will be classified as a hypoglycemic AE if the answer to the question "Is this a hypoglycemic event?" is Yes on the AE CRF page.

4) Injection Site Reactions

Injection site reactions will be identified using the High Level Term = "Injection site reactions".

5) IP-related adverse events

An AE will be classified as related to IP if the relationship to study treatment is Possibly Related, Probably Related, or Definitely Related. Additionally, if the relationship is missing, then the AE will be deemed related to IP.

6) Measured Hypoglycemic AE

A hypoglycemic AE will be classified as measured if the lowest blood glucose value documented on the Hypoglycemia page is less than or equal to 3.0 mmol/L.

7) Persistent/Non-persistent Hypoglycemic AE

Hypoglycemic event with Time in hypoglycemia (see definition in Section 7.4) greater or equal to an hour (per CGM) would be classified as persistent. A hypoglycemic event with Time in hypoglycemia below an hour (per CGM) would be classified as non-persistent.

8) Symptomatic Hypoglycemic AE

A Hypoglycemic AE will be classified as symptomatic if the answer to the question "Was subject aware of symptoms?" is Yes on the Hypoglycemia CRF page.

9) Treatment-emergent adverse events (TEAE)

A TEAE is defined as an AE occurring on or after the date of the subject's first dose of IP and on or before the day of last dose for AEs but not more than 30 days after the subject's last dose of IP for SAEs.

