#### **8.7.3.2 Safety**

- The incidence and severity of all treatment-emergent adverse events and the following subgroups:
  - Hypoglycemia, which will be fully documented prospectively in the Hypoglycemic Events Record
  - Serious adverse events, including fatal events

- Adverse events leading to termination of the study treatment and/or early withdrawal from the study
- IP-related adverse events
- Injection site reactions
- The incidence of clinically significant laboratory abnormalities
- The incidence of clinically significant abnormalities in ECG and vital signs

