## **12.8 Key Secondary Endpoint**

### **12.8.1 Change from Baseline in HbA1c at 26 Weeks**

The key secondary analysis will be to evaluate equivalence (FDA)/noninferiority (EMA) of Gan & Lee Insulin Glargine Injection relative to Lantus® for HbA1c by comparing the 90% CI with (-0.4%, 0.4%) for equivalence using the TOST approach and by comparing the upper limit of the 95% CI with 0.4% for noninferiority from a pattern mixture model that uses multiple imputation analyzed using Analysis of Covariance (ANCOVA) with treatment included as a fixed effect and baseline HbA1c included as a covariate. Separately in each treatment group, the imputation will use the outcomes of patients who completed the study (including the subjects who discontinued treatment, but provided a visit Week 26 HbA1c sample) to impute outcomes in patients without actual visit Week 26 recorded results under the missing at random assumption. Full details of the multiple imputation procedure will be specified in the SAP. Analysis of HbA1c will follow a hierarchical testing strategy: first, equivalence/noninferiority will be tested with a margin of 0.4%; secondly, if and only if the test using a margin of 0.4% is significant, then equivalence/noninferiority will be tested using a margin of 0.3%. Analyses of HbA1c in the testing hierarchy will be conducted on the Full Analysis Set consisting of all randomized subjects according to randomized treatment with supportive analyses on the Per Protocol Analysis Set. A tipping point analysis with varying assumptions about the differences on each treatment arm between outcomes in patients who withdrew from the study early and outcomes in patients who completed the study will be performed. The estimand of interest for the HbA1c analysis is the difference in change from baseline for HbA1c using the “treatment policy strategy.”

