3.1 Changes from Protocol

Per FDA comment, Wald method has been replaced with logistic regression approach to calculate the difference in proportions along with the corresponding 90% CI for the primary endpoint and corresponding sensitivity analyses. The delta method will be used to calculate the standard error for the difference and the associated confidence interval.

Also, per FDA suggestion, separately in each treatment group, the imputation will use outcomes in patients who discontinued treatment but provided a visit Week 26 glycosylated hemoglobin (HbA1c) measurement if sufficient data are available to impute outcomes in patients without actual visit Week 26 recorded results, under the assumption of missing not at random (MNAR). Full details are provided in Section 11.7 below.

4. Study Objectives

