7.1 General

1) Actual Treatment

The actual treatment received is defined as the IP treatment the subject received during the study, regardless of the treatment the subject was allocated to by randomization. If a subject receives both Gan & Lee Insulin Glargine Injection and Lantus® during the study period for whatever reason, then the actual treatment will be based on the treatment taken on the majority of days during the study.

2) Assessment after EOT

Assessment after EOT is defined as AIA/HbA1c assessment documented after date of EOT visit. If date of EOT visit is missing it is defined as assessment documented after date of last dose of IP + 1 day (to consider assessments of subjects who perform the visit assessment before daily dose of IP).

3) Average Daily Dose of IP

Average Daily Dose is defined as captured on the Average Daily Dose of Study Drug CRF page.

4) Baseline

For each endpoint of interest, unless otherwise noted, the study baseline is defined as the last non-missing assessment taken prior to or on the date of the first dose of study IP. For subjects whose treatment assignment is randomly assigned but not dosed after the randomization visit, the baseline is defined as the last non-missing assessment prior to or on the date of randomization.

5) Change from Baseline

Change from baseline is defined as (value at post-baseline visit – value at baseline).

6) Completer Week 26

A subject is defined as a Completer Week 26 if the answer to the question "Did the subject complete the study?" is "Yes" on the End of Study CRF page and who received IP for at least 22 weeks.

7) Dates of First and Last Dose

The date of first dose of IP is defined as the date of first dose of IP documented on the First Dose of Study IP CRF page and the date of last dose of IP is defined as the date of last dose of IP documented on the End of Study 2 CRF page. If no date of first dose of IP is available, the date of randomization will be selected as the date of first dose of IP. If no date of last dose of IP is available, the date of completion/discontinuation documented on the End of Study CRF page will be selected as the date of last dose. If date of last dose of IP is not available and subject is lost to follow up based on End of Study CRF page, date of last scheduled visit or date of last telephone contact where an average daily dose is recorded, will be used as the date of last dose of IP.

8) Diabetes Disease Duration

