Any subject who discontinues from treatment before visit Week 26 (Visit 9) will have the Visit 9 procedures performed for their EOT visit. This will be captured in the CRF under visit Week 26 and will be presented by scheduled time point tables together with Week 26 results for subjects who completed the study. Whereas no visit window will be applied for most of the visit, visit window will be considered for Week 12 or 26 visit AIA assessment only (and visit window will be considered for Week 26 visit HbA1c assessment only) if the visit is within the visit window (week 12 \pm 1 week or week 26 \pm 4 weeks). Subjects are encouraged to come back for assessments at Week 12 and Week 26 even if they have discontinued treatment early.

Subjects treated according to previous protocol version who have data recorded at visits > visit Week 26, will have those data listed only.

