11.8.1 Treatment Emergent Adverse Events

An overall summary of TEAEs (defined in Section 7.3) will be presented, including the number of events reported, the number and percentage of subjects with at least one of the following (Table 6, Analysis 3):

- Adverse event
- Grade ≥ 3 TEAE
- Hypoglycemic TEAE
- Severe hypoglycemic TEAE
- IP-related AE

Sponsor: Gan & Lee Pharmaceuticals, USA Corporation
Protocol no: GL-GLAT2-3002

Statistical Analysis Plan
Version Date: 16-Nov-2020

- Grade \geq 3 IP-related AE
- Death
- SAE
- IP-related SAE
- Hypoglycemic SAE
- AE leading to discontinuation of IP
- IP-related AE leading to discontinuation of IP

To evaluate the potential impact of eligibility related important protocol deviations on subject safety, an overall summary of TEAEs will also be presented by presence / absence of ERIPD. ERIPDs are those coded to the Inclusion Criteria or Exclusion Criteria categories (refer to Section 7.1, 11.3 and Appendix 4 for details). Additionally, safety analyses of ERIPD interaction with treatment group will be performed in logistic regression models adjusted by country. The interaction term estimates, 90% CI and p-value from these interaction analyses will be presented with the number and percentage of subjects with the following TEAEs by presence / absence of ERIPD under each treatment arm:

- Adverse event
- Grade \geq 3 AE
- Hypoglycemic AE
- Severe hypoglycemic AE

A fragment of the SAS code for the interaction analysis is provided below for reference.

```
proc logistic data=<data>;
  class trt ERIPD/ param=ref ref='Lantus';
  model response=trt ERIPD trt*ERIPD;
run;
```

A breakdown of the number and percentage of subjects reporting each AE, categorized by System Organ Class (SOC) and preferred term coded according to MedDRA, will be presented. Note that counting will be by subject (not event), and subjects are counted only once within each SOC or preferred term. Sorting will be in descending frequency for SOC and descending frequency for preferred term within SOC in the total column.

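### The SAP's flag for AEs leading to discontinuation of IP is built from a CRF item about leaving the study, so AEs that ended treatment only can be missed

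*SAP*

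**What the plan says.** The endpoint is the same in both documents. Protocol 8.7.3.2 lists it as "Adverse events leading to termination of the study treatment and/or early withdrawal from the study", SAP 6.3.2 repeats it, and the protocol synopsis and Section 12.9.2 have the same scope.

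The SAP's operational rule is in Section 7.3, definition 2. It begins "An AE will be classified as an AE leading to discontinuation of IP if the answer to the question" and then gives the AE-page item: "Did the adverse event cause the subject to be discontinued from the study". A Yes sets the flag, and nothing else does.

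SAP 11.8.1 uses the flag in the overall TEAE summary, in the tables by preferred term and in a listing. A second version is restricted to related events: "IP-related AE leading to discontinuation of IP".

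**The concern.** The label and the item describe different things. The item asks whether the AE took the subject out of the study. The variable name says the AE stopped the product. In a trial where stopping IP always meant leaving the study, this would be loose wording only. Here both documents provide for subjects who come off treatment and still return for samples, so the two states can differ.

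At stake is a named secondary safety endpoint on tolerability. A subject who stops IP because of, say, an injection site reaction but goes on providing data could be answered No. The AE would still appear in the general TEAE tables, but not as one that ended treatment. The clinical study report would then carry a row headed discontinuation of IP that does not measure it.

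**Working it through.** The documents give no figure to reproduce, so the check sets the texts side by side.

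**1. Endpoint against item.** There are four possible cases for an AE:

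| AE ended IP | AE ended study participation | In the endpoint | Flagged by SAP 7.3(2) |
|---|---|---|---|
| Yes | Yes | Yes | Yes |
| Yes | No | Yes | No |
| No | Yes | Yes | Yes, under the IP label |
| No | No | No | No |

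The exposed case is the second row. The question is whether the documents allow it.

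**2. Can a subject stop IP without leaving the study?**

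- Protocol 12.8.1 describes the subjects who completed the study as "including the subjects who discontinued treatment, but provided a visit Week 26" HbA1c sample. This is the most direct evidence, because a subject off treatment is counted as a study completer.
- SAP 3.1 bases the main HbA1c imputation on "patients who discontinued treatment but provided a visit Week 26 glycosylated hemoglobin (HbA1c) measurement", and SAP 11.7.1.1 implements it.
- The general text of SAP Section 11, just before 11.1, says "Subjects are encouraged to come back for assessments at Week 12 and Week 26 even if they have discontinued treatment early".
- SAP 11.6.1.1 treats stopping study treatment as an intercurrent event and uses AIA data collected after it.
- SAP 7.1(6) defines Completer Week 26 by completion of the study "and who received IP for at least 22 weeks". This fits with the two being separate but does not prove it. The SAP gives no reason for the condition, and 22 weeks is also the lower edge of the Week 26 window: 182 − 28 = 154 days = 22 × 7.

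So the second row is possible.

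**3. Does anything else in the SAP pick up these AEs?**

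- Protocol 11.1 says an action is recorded for each AE, illustrated by treatment and follow-up tests. The SAP definition does not use it, and the CRF is not among the documents.
- The End of Study reasons in SAP 11.2 concern withdrawal from the study, so they cannot identify treatment-only stops.
- The last-dose date in SAP 7.1(7) shows when IP stopped, not why.

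Nothing recovers the second row.

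**4. Size.** Let n be the number of AEs that ended IP, and s the share of them answered No to the study item. Then

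- counted by the rule = n(1 − s)
- missed = n·s

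At s = 0 all are counted; at s = 1 none are. The documents give neither n nor s.

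**The case against.** The strongest reply is that stopping IP for an AE and leaving the study largely coincide under this protocol:

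- Protocol 8.4.3.1 deals with an intolerable AE as a withdrawal from the study, with study medication stopped at the same time.
- Exclusion criterion 6 says a change in type or brand of insulin leads to withdrawal, and 8.4.3.1 lists it as a withdrawal reason. A subject who leaves IP for another basal insulin would meet that rule.
- Protocol 10.4 requires withdrawal for clinically relevant cardiovascular adverse events.
- Protocol 8.1, footnote a of Table 1 and Section 9.11 address the return visits to subjects who discontinue or withdraw from the study. A subject who comes back for samples may already have a Yes.
- SAP 7.1(25) censors everyone who completed the study when timing early treatment discontinuation, which treats the two as one event.
- SAP 5.1 attributes the return-visit procedures to Amendment 3, dated 25 April 2019. SAP 10.3 puts the last follow-up at 13 August 2019, so those procedures ran for at most 110 days.
- The tables are descriptive, the same rule applies in both arms, and the events stay visible in other AE tables.

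Most of this stands, and it limits the likely effect. It does not repair the definition. The return visits are described in one place for subjects who leave the study (Protocol 9.11) and in another for subjects who stop treatment (general text of SAP Section 11). The answer for a retained subject therefore depends on how each site reads the item. Protocol 12.8.1 still allows a study completer who is off treatment. Even with no AE missed, the label would state something that was not asked.

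**Conclusion.** The point holds as a mismatch between endpoint, label and source item. SAP 7.3(2) captures the study-withdrawal component and reports it as the treatment component, and AEs that ended IP only can be missed. It should be corrected before lock. It affects a descriptive secondary safety endpoint, not the AIA or HbA1c analyses.

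A reader might go further and infer that the rate of AE-driven IP stops is understated, or understated by a material share, among the subjects the trial tried to retain. The documents do not support that. They report no count of AE-driven IP stops, no split between treatment-only and study discontinuation, and no answers to the item. SAP 5.1 says early discontinuation was higher than expected, but not how much of it was due to AEs. The shortfall may be small or zero.

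The conclusion rests on two assumptions: that the item is answered as worded, and that no derivation outside the SAP supplements it. The CRF was not available to check either.

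**What to change.** 1. Rename the variable in SAP 7.3(2) as AE leading to study discontinuation, keeping its present source item.
2. Define AE leading to discontinuation of IP separately. If the AE page has a field for action taken with IP, use it.
3. If it does not, review AEs before lock and without regard to treatment assignment, in subjects whose duration of therapy (SAP 7.1(13)) is under 22 weeks and who have no Yes on the current item. Record whether an AE ended IP. The blinded data review meeting in SAP 10.2 is a natural place for this.
4. Report three rows: AE ending IP, AE ending study participation, and their union, which is the endpoint as written. Do the same for the IP-related version, and carry it into the preferred-term tables and the listing.
5. If the review is not done, state in the SAP and in table footnotes that treatment-only stops are not captured.

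The 22-week trigger is the SAP's own threshold. A trigger of last dose before the EOT visit would be too broad, because completers who attend before their daily dose would be flagged. The threshold has two limits that should be stated. It does not flag stops in the last four weeks. It can also miss subjects with no recorded last-dose date, for whom SAP 7.1(7) may substitute the End of Study date; these are best added to the review list.

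The cost is SAP wording, a short masked review and a few table rows. No new data collection is needed.

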7.4 Exploratory

1) Continuous Glucose Monitoring Device Day of Wear

The Day of wear will be defined as starting exactly $(x-1)*24$ hours and ending $x*24$ hours after the time of the first assessment at the given visit, where x is the Day of wear from 2 to 8 days.

Sponsor: Gan & Lee Pharmaceuticals, USA Corporation
Protocol no: GL-GLAT2-3002

Statistical Analysis Plan
Version Date: 16-Nov-2020

2) Time in hypoglycemia

The time in hypoglycemia will be defined using the CGM data from days 2 through 8 of wear at each of the 3 visits where CGMs are applied as the sum of the time where the glucose value is ≤ 3.0 mmol/L.

$$\sum_{i=1}^{n_T} I_{GC_i}(t_{i+1} - t_i)$$

where I_{GC_i} represents the indication of whether or not the glucose concentration at time i is ≤ 3.0 mmol/L, t_i represents the i^{th} time point (the difference between each time point will be 15 minutes), and n_T represents the number of time points for a given subject and visit and can vary based on subject and visit.

3) Time in hyperglycemia

The time in hyperglycemia will be defined using the CGM data from days 2 through 8 of wear at each of the 3 visits where CGMs are applied as the sum of the time where the glucose value is ≥ 8.9 mmol/L.

$$\sum_{i=1}^{n_T} I_{GC_i}(t_{i+1} - t_i)$$

where I_{GC_i} represents the indication of whether or not the glucose concentration at time i is greater than or equal to 8.9 mmol/L, t_i represents the i^{th} time point (the difference between each timepoint will be 15 minutes), and n_T represents the number of time points for a given subject and visit and can vary based on subject and visit.

4) Time in euglycemia

The time in euglycemia will be defined using the CGM data from days 2 through 8 of wear at each of the 3 visits where CGMs are applied as the sum of the time where the glucose value is >3.0 mmol/L and < 8.9 mmol/L.

$$\sum_{i=1}^{n_T} I_{GC_i}(t_{i+1} - t_i)$$

where I_{GC_i} represents the indication of whether or not the glucose concentration at time i is >3.0 mmol/L and <8.9 mmol/L, t_i represents the i^{th} time point (the difference between each time point will be 15 minutes), and n_T represents the number of time points for a given subject and visit and can vary based on subject and visit.

8. Analysis Sets

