11.7.3 Exploratory Variables

11.7.3.1 Retrospective Hypoglycemic Rate

In addition to the analysis of hypoglycemic events from the AE data, a retrospective analysis of the CGM data will be performed to identify hypoglycemic events that may have gone unnoticed by the subject (Table 6, Analysis 1). A retrospective CGM-hypoglycemic event will be defined as anytime the glucose concentration decreases below the threshold of ≤ 3.0 mmol/L. This definition is supported by Seaquist et al (8). Multiple hypoglycemic events while a subject is wearing the CGM device may occur and are defined as having a glucose concentration that returns to > 3.0 mmol/L before decreasing below the threshold again. The number of hypoglycemic events detected between days 2 through 8 of CGM wear for each subject at each visit will be summarized descriptively in the SS. A listing of the CGM-hypoglycemic events including the lowest glucose concentration during the event will be provided.

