A summary of ADA severe hypoglycemia TEAEs, symptomatic hypoglycemia TEAEs and measured hypoglycemia TEAEs will be produced, presenting the number and percentage of subjects with at least one event, as well as of the number and percentage of subjects with no events, at least one event, 1 event, 2 events, and 3 or more events (Table 6, Analysis 15). Persistent and non-persistent TEAEs will be summarized, presenting subjects with no event and at least one event (Table 6, Analysis 12).

Symptomatic or measured hypoglycemic TEAEs will be summarized by site, treatment group and overall, presenting the number of events reported, the number and percentage of subjects with at least one event (Table 6, Analysis 13). Sites with fewer than 8 subjects will be combined for summaries and analyses. A further summary by treatment group and overall will report the number and percentage of subjects with no events, at least one event, 1 event, 2 events, and 3 or more events (Table 6, Analysis 12).

All hypoglycemic events recorded on the Hypoglycemia CRF page will be listed for subjects in the SS. Additionally summary of ADA graded hypoglycemic event and TEAE by ERIPD subgroup will be produced for per protocol analysis set 2 and 3 (Table 6, Analysis 16).

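### SAP 7.3 labels a hypoglycemic AE persistent from the subject's seven-day CGM total rather than from the length of that event, and gives no rule linking AEs to CGM windows

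*SAP*

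**What the plan says.** - **SAP 7.3 Safety, definition 7** sets the rule. An event whose Time in hypoglycemia, with an explicit pointer to Section 7.4 for that term, is "greater or equal to an hour (per CGM) would be classified as persistent". The complement is: "A hypoglycemic event with Time in hypoglycemia below an hour (per CGM) would be classified as non-persistent".
- **SAP 7.4 Exploratory, definition 2** supplies the quantity. It is computed "using the CGM data from days 2 through 8 of wear at each of the 3 visits where CGMs are applied", and is taken "as the sum of the time where the glucose value is" at or below 3.0 mmol/L. The formula adds the 15-minute intervals over all time points of a given subject and visit. It has no index for an event and no requirement that low readings be consecutive.
- **SAP 7.3, definition 3** says what is being labelled. An AE is hypoglycemic if the AE CRF page says so.
- **SAP 11.7.3.1** treats CGM events as a separate object: "Multiple hypoglycemic events while a subject is wearing the CGM device may occur", with a return above 3.0 mmol/L dividing one from the next. It gives these events no duration, and definition 7 does not refer to it.
- **SAP 11.8.1.1** reports the result under Table 6, Analysis 12: "Persistent and non-persistent TEAEs will be summarized, presenting subjects with no event and at least one event".

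**The concern.** Persistence is a property of one event, but the quantity behind the label belongs to a subject and a week. If the cross-reference is programmed as written, a short reported AE can be called persistent because of low readings on other days that have nothing to do with it. A programmer who instead guesses at per-event duration would produce a different table from the same data.

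Hypoglycemia is a listed secondary safety endpoint (SAP 6.3.2) and the protocol's adverse event of special interest (Protocol 11.3), so the split should mean what its label says.

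There is a second gap. The rule needs CGM data for each AE, but the SAP does not say how an AE recorded on the CRF is assigned to a CGM window, or what happens to an AE that falls outside every window.

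**Working it through.** The plan gives no figure for this definition, so there is nothing to reproduce. The check applies the SAP 7.4 formula to constructed readings.

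**Inputs**
- Cut-off: 60 minutes (SAP 7.3, definition 7).
- Reading interval: 15 minutes. Low means at or below 3.0 mmol/L (SAP 7.4).
- Window: days 2-8 of wear, which is 7 days per CGM visit (SAP 7.4).
- Boundary between CGM events: return above 3.0 mmol/L (SAP 11.7.3.1).
- Treatment period: 26 weeks, with post-baseline CGM before the Week 12 and Week 26 visits (Protocol 8.1).

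**Step 1: what the cut-off requires**

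Readings per day = 24 × 60 / 15 = 96. Readings per window = 7 × 96 = 672. Low readings needed = 60 / 15 = 4, and 4 / 672 = 0.6% of the window. They may fall anywhere in it.

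**Step 2: the total against the episode**

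| Low readings in the window | SAP 7.4 total | Label from total | Episode lengths | Label by episode |
|---|---|---|---|---|
| 15-min event and three 15-min dips on other days | 60 min | persistent | 15, 15, 15, 15 | none persistent |
| 45-min event and one 15-min dip on another day | 60 min | persistent | 45, 15 | none persistent |
| One continuous 60-min event | 60 min | persistent | 60 | persistent |
| One 45-min event alone | 45 min | non-persistent | 45 | non-persistent |

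The total is never smaller than any episode it contains. Within an analysed window the error therefore runs one way: an episode of 60 minutes or more lying in the window cannot be labelled non-persistent, but shorter ones can be labelled persistent.

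**Step 3: how often scattered dips could do this**

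The documents give no frequency of low readings. As an assumption only, let isolated 15-minute dips unrelated to the reported AE be Poisson with mean m per window.
- If the AE itself contributes one low reading, three other dips suffice: P = 1 − e^(−m)(1 + m + m²/2).
- If the AE contributes none, four are needed: P = 1 − e^(−m)(1 + m + m²/2 + m³/6). This can happen because Grade 1 events in SAP Table 7 run from 3.0 up to 3.9 mmol/L.

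| m | Three or more other dips | Four or more other dips |
|---|---|---|
| 1 | 1 − 0.3679 × 2.5 = 8% | 2% |
| 2 | 1 − 0.1353 × 5 = 32% | 14% |
| 3 | 1 − 0.0498 × 8.5 = 58% | 35% |
| 4 | 1 − 0.0183 × 13 = 76% | 57% |
| 6 | 1 − 0.00248 × 25 = 94% | 85% |

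The range is wide. It shows only that the effect depends on how often subjects dip, not how large it was in this trial.

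**Step 4: coverage**

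Post-baseline analysed CGM days = 2 × 7 = 14. Treatment days = 26 × 7 = 182. Coverage = 14 / 182 = 7.7%. The screening window precedes the first dose, so it cannot contain a treatment-emergent event. On the other 168 days an AE has no CGM time of its own in the analysis, and the SAP gives no rule for it.

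**The case against.** The best defence is that definition 7 speaks of an event with a certain time in hypoglycemia. That can be read as the event's own time, with SAP 7.4 supplying only the 3.0 mmol/L threshold and the interval-counting rule. The table shells are a separate document (SAP Appendix 3) and may settle it. This stands in part: per-event duration may well have been intended. But the cross-reference is explicit, the SAP 7.4 formula is a subject-visit total, and neither document defines a duration for a single event. The text needs correcting on either reading.

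A reader might infer more, namely that scattered CGM dips are themselves reported as persistent hypoglycemia, so that four dips become four persistent events. The documents do not support that. The label applies to AEs flagged on the CRF, and SAP 11.8.1.1 also drops those with a blank or missing Hypoglycemia page. SAP 6.3.2 lists CGM among the sources for hypoglycemia, but the CRF answer remains the criterion. The sensor is blinded to the subject (Protocol 8.1), and the retrospective CGM analysis in 11.7.3.1 is separate. An unreported dip matters only by adding minutes to a week in which an AE was reported.

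Nor does the split lose all meaning. The total is still a duration, the last two cases in Step 2 are labelled alike under both rules, and the output counts subjects, so several mislabelled events in one subject count once. The same rule applies to both arms, the summary is descriptive, and no test uses it.

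**Conclusion.** The point holds as a definition error with limited consequences. Read literally, a brief reported hypoglycemic AE in a CGM week is called persistent whenever the week's low readings reach 60 minutes, which any 4 of 672 readings achieve. The persistent/non-persistent TEAE summary can therefore over-count subjects with persistent events.

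This rests on two assumptions: that the SAP 7.4 reference is programmed as written, and that the AE is assigned to the window in which it falls. The over-counting direction applies only inside an analysed window. Outside one, about 92% of treatment days, the label is undefined, and a default of zero CGM minutes would push AEs into the non-persistent group without evidence. The actual number of subjects affected cannot be derived from the documents.

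Severity is low. The primary immunogenicity analysis and the key secondary HbA1c analysis do not use this definition.

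**What to change.** Amend definition 7 in SAP 7.3 before database lock:

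1. Replace the SAP 7.4 total with the duration of the single CGM episode that matches the AE in date and time. Delimit the episode as in 11.7.3.1, by return above 3.0 mmol/L.
2. Compute that duration by applying the SAP 7.4 interval formula within the episode, so that four consecutive low readings count as 60 minutes. Say so explicitly: four readings span only 45 minutes from first to last, and without a convention a programmer might require five. Keep the existing one-hour cut-off.
3. State the AE-to-episode matching rule, including the time tolerance, the handling of AEs with a missing time, and the treatment of an AE that has sensor data but no reading at or below 3.0 mmol/L.
4. Report AEs with no matching CGM data as *not classifiable*, as a third row in the summary under Table 6, Analysis 12.

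The cost is a few sentences, one extra table row and some programming. No new data are needed: sensor readings are held, and Protocol 11.1 already asks for the time and duration of each AE.
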